1.0 Objectives

1.1 The overall purpose and objective of this project is to test the hypothesis that high intensity endurance exercise causes beneficial brain adaptation in patients with mild cognitive impairment in Parkinson's disease (PD-MCI). Aim 1 will determine the effect of high intensity endurance exercise on cognitive function and other clinical symptoms in PD-MCI. Aim 2 will determine the effect of high intensity endurance exercise on brain structure and function in PD-MCI. Aim 3 will determine the effect of high intensity endurance exercise on cortisol in PD-MCI. Aim 4 will determine the effect of high intensity endurance exercise on inflammation-related biomarkers found in blood in PD-MCI. Aim 5 will determine the effect of high intensity endurance exercise on peripheral levels of neurotrophic factors found in blood in PD-MCI.

1.2 Hypothesis 1 is that high intensity endurance exercise will improve cognitive function, specifically attention, executive function and memory in PD-MCI patients. In addition, high intensity endurance exercise will improve other PD-related symptoms such as sleep, fatigue, mood, health-related quality of life, and motor function.

Hypothesis 2 is that high intensity endurance exercise will modify brain structure and function as measured by structural MRI, diffusion tensor imaging (DTI), and resting state functional MRI (rsfMRI), specifically by: a) increasing hippocampal volume, b) increasing microstructural integrity of white matter pathways connecting different brain regions (e.g., fronto-striatal, fronto-parietal, and hippocampal regions, and c) enhancing functional connectivity among brain networks (e.g., default mode and central executive networks).

Hypothesis 3 is that high intensity endurance exercise will lead to decreased levels of cortisol and an increase in the magnitude of the cortisol awakening response (CAR).

Hypothesis 4 is that high intensity endurance exercise will lead to decreased levels of inflammation suggested by a decrease in levels of inflammation-related biomarkers found in blood.

Hypothesis 5 is that high intensity endurance exercise will lead to increased levels of peripheral neurotrophic factors.

2.0 Background

2.1 There is a growing interest in physical exercise as a treatment for PD symptoms and ultimately as a potential disease modification strategy. Most PD exercise studies have focused on motor function (Salgado, Williams et al. 2013), though our group also found improved executive function after balance/strengthening and progressive resistance training. (Corcos, Robichaud et al. 2013, David, Robichaud et al. 2015) The knowledge gap is that no study has specifically targeted PD-MCI patients to determine how exercise affects cognitive functions or the underlying neurobiology of PD-

PROTOCOL TITLE: Mild Cognitive Impairment and Endurance Exercise in Parkinson's Disease

MCI. Thus, the central hypothesis is that high intensity endurance exercise not only will improve the cognitive function of patients with PD-MCI, but also will produce neurobiological changes in their brain and body.

We have just finished collecting data on the effect of high intensity endurance exercise regimens on parkinsonian motor signs in 129 never medicated patients with PD. Patients exercised 4 days a week at either 65% of their maximal heart rate or at 80% of their maximal heart rate. As such, we have considerable experience in using endurance exercise protocols.

- 2.2 We have no preliminary data for this study. The purpose of this IRB is to collect pilot data for a subsequent R01.
- 2.3 Parkinson's disease (PD) is a neurodegenerative disorder that affects over 4 million people older than age 50.(Dorsey, Constantinescu et al. 2007) While the motor features of PD are well-recognized and well-treated with dopaminergic medications, PD is also complicated by non-motor symptoms, which cause significant disability, lack effective therapies, and typically do not respond to dopamine replacement therapy. One of the most disabling non-motor symptoms in PD is cognitive impairment, which ranges from mild deficits to severe dementia.(Emre, Aarsland et al. 2007, Hely, Reid et al. 2008, Litvan, Goldman et al. 2012) In recent years, mild cognitive impairment (PD-MCI) has been identified as a frequent occurrence in PD and a precursor to PD dementia, which can develop in 80% of PD patients over time.(Hely, Reid et al. 2008, Litvan, Aarsland et al. 2011, Litvan, Goldman et al. 2012) Recent research has characterized the cognitive deficits of PD-MCI, developed diagnostic criteria, and identified neuroimaging markers of PD-MCI.(Goldman, Stebbins et al. 2012, Goldman, Holden et al. 2013, Goldman, Holden et al. 2015) However, there are currently no therapeutic interventions that can effectively improve the symptoms of PD-MCI or slow down or halt cognitive decline in PD.(Goldman and Weintraub 2015)

While PD-MCI is a relatively new concept within the PD field, the idea of MCI as a state between normal cognitive aging and Alzheimer's disease has been recognized for many years and has led to treatment trials with pharmacological and non-pharmacological interventions, including physical exercise training. For example, Baker and colleagues (2010) have shown improved executive function in women with MCI and improved performance on the Trail B in men as a result of endurance exercise at between 75% and 85% heart rate reserve. Indeed, studies of exercise training, with a variety of techniques (e.g., endurance [also called aerobic], resistance, balance and tone training) demonstrate improvement in cognitive functions of MCI (non-PD) patients, as well as in some studies, other symptoms such as mood, sleep, fatigue and health-related quality of life.(Wang, Yu et al. 2014) Exercise also exerts neurobiological effects, as seen in animal models of exercise,(Silverman and Deuster 2014, Petzinger, Holschneider et al. 2015, Duzel, van Praag et al. 2016)as well as human studies of aging and MCI utilizing neuroimaging and other peripheral

PROTOCOL TITLE: Mild Cognitive Impairment and Endurance Exercise in Parkinson's Disease

biomarkers.(Voss, Prakash et al. 2010) Endurance exercise, in particular, has been linked to brain plasticity with magnetic resonance imaging (MRI) scans revealing structural changes (e.g., increased volume in the hippocampus, a key brain region for memory) and functional changes (e.g., increased connections among brain networks involved in cognitive processes) in aging adults and MCI patients.(Voss, Prakash et al. 2010, Erickson, Voss et al. 2011, ten Brinke, Bolandzadeh et al. 2015) Endurance exercise at between 65% and 75% maximal heart rate reserve can enhance the mental aspect of both health-related quality of life (HRQOL) and also global quality of life (global HQL).(Awick, Wojcicki et al. 2015)

Exercise can affect neurobiological markers of stress (e.g., cortisol), inflammation (e.g., cytokines) and growth factors (e.g., brain-derived neurotrophic factor [BDNF], insulin-like growth factor [IGF-1]), and these peripheral markers may mediate exercise effects on brain structure and function. (Foster, Rosenblatt et al. 2011, Voss, Vivar et al. 2013). Cortisol is released during exercise as a contributory factor to both muscular and mitochondrial function. Aside from the influential effects of cortisol on the muscular system, the release of cortisol during exercise also modulates different neurotransmitters and influences both cognition and neuroplasticity. (Diamond, Bennett et al. 1992, Piazza, Rouge-Pont et al. 1996, Joels and Krugers 2007, Sousa, Cerqueira et al. 2008, Mora, Segovia et al. 2012) Cortisol receptors can be found in brain regions involved in cognitive processing, such as the neocortex, cerebellum, and the hippocampus (Heffelfinger and Newcomer 2001) and it is widely recognized that glucocorticoids easily enter the brain and exert effects on cognition (de Quervain, Aerni et al. 2009). Cortisol levels in healthy elderly adults studied over a period of five years revealed that individuals with high basal cortisol levels and increasing cortisol levels over five years had hippocampal-dependent memory impairments and a 14% reduction in hippocampus volume when compared with individuals who either had moderate basal cortisol levels or decreasing cortisol levels over the five-year period.(Lupien, Fiocco et al. 2005) Flatter diurnal cortisol slopes have been associated with a decline over 4 years in visuospatial performance and visual memory in men, and in verbal fluency for women.(Beluche, Carriere et al. 2010) In the extreme, no morning cortisol response has been observed a 6 male patients with amnesia,(Wolf, Fujiwara et al. 2005) and also in patients with hippocampal damage.(Buchanan, Kern et al. 2004) In older adults diagnosed with MCI, the magnitude of the CAR and the extent of the subsequent drop in cortisol levels are both associated with level of fitness.(Tortosa-Martinez, Clow et al. 2015) It was shown that a three month exercise program improved fitness, increased the fall in cortisol concentration from the morning peak to midday, and enhanced indices of executive function in older adults with MCI. (Tortosa-Martinez, Clow et al. 2015). Earlier peaking and greater magnitude of the CAR has also been associated with superior performance on executive function related tasks in older adults.(Evans, Hucklebridge et al. 2012) To the best of our knowledge,

PROTOCOL TITLE: Mild Cognitive Impairment and Endurance Exercise in Parkinson's Disease

the CAR has not been measured in individuals with Parkinson's disease. Because the cortisol awakening response is distinct from circadian components of cortisol control, assessment of the CAR in individuals with PD may provide additional insight into additional neuroendocrine processes that other cortisol measures may not. (Stalder, Kirschbaum et al. 2016)

There is increasing evidence that inflammation is a contributing factor to both the pathogenesis and progression of PD (Beal, 2003; Chung et al., 2010; Sawada, Imamura, & Nagatsu, 2006). Chronic inflammation mediated by microglial cells is a fundamental process contributing to the death of dopamine-producing neurons in the brain, and it is suggested that physical stress may facilitate the progression of neurodegenerative disorders such as PD (Sugama, 2009). Regular physical activity tends to result in lower serum concentrations of inflammatory markers (Kasapis & Thompson, 2005). Chronic exercise training is thought to reduce levels of inflammatory markers both directly by attenuating cytokine production by adipose tissue, skeletal muscle, and mononuclear cells, and indirectly through improved insulin sensitivity and endothelial function, decreased body weight, and by upregulating antioxidant enzymes (Kasapis & Thompson, 2005).

Neurotrophic factors (NFs) are a family of proteins that play a significant role in the growth, survival, and maintenance of neurons (Rangasamy, Soderstrom, Bakay, & Kordower, 2010). Different proteins such as brain-derived neurotrophic factor (BDNF), glial cell-derived neurotrophic factor (GDNF), insulin-like growth factor (IGF), and vascular endothelial growth factor (VEGF) have been classified as NFs, due to their ability to effect neuronal survival, differentiation, and maturation, and synaptogenesis (da Silva, Domingues, de Carvalho, Allodi, & Correa, 2016). Many studies have demonstrated the influence of trophic factors on neuroprotection, neurorestoration, and functional improvement in both PD animal models and some human clinical trials (Rangasamy et al., 2010). It has been suggested that NFs influence cell survival and restoration of dopaminergic cells in the nigrostriatal pathway (Petzinger et al., 2007; Tajiri et al., 2010; Tillerson, Caudle, Reveren, & Miller, 2003; Yoon et al., 2007).

The exercise-induced benefits of improved brain plasticity, function, and health can be at least partially attributed to growth factors, primarily BDNF, IGF-1, VEGF, and GDNF (Cotman et al., 2007; Knaepen, Goekint, Heyman, & Meeusen, 2012).

3.0 Inclusion and Exclusion Criteria

PROTOCOL TITLE: Mild Cognitive Impairment and Endurance Exercise in Parkinson's Disease

3.1 Individuals will be screened for eligibility as follows. Participants will meet the criteria outlined below. Participants will be assessed for eligibility criteria by the PI and study team via telephone screening after referral by the Neurologist. The screening will last approximately 30 minutes. A telephone script will be used to screen participants.

3.2 Inclusion criterion:

- Male or female, ages 40-85
- A diagnosis of idiopathic PD based on the UK PD brain bank criteria.(Hughes, Ben-Shlomo et al. 1992, Hughes, Daniel et al. 1992, Hughes, Ben-Shlomo et al. 2001)
- A diagnosis of PD-MCI as determined by the Movement Disorder Society (MDS) Task Force PD-MCI diagnostic criteria (Litvan, Goldman et al. 2012) and a SCOPA-Cog score of 17-24 (Marinus, Visser et al. 2003, Isella, Mapelli et al. 2013, Marras, Armstrong et al. 2013)
- Hoehn and Yahr stage < or equal to 3
- Stable medication regimen for > or equal to 30 days before entering the study
- Living with a carepartner

Exclusion criterion:

- PD subjects meeting MDS criteria for PD dementia (Emre, Aarsland et al. 2007) or having a SCOPA-Cog score less than or equal to 16, or PD subjects having normal cognition defined as a SCOPA-Cog Score of greater or equal to 25.
- Atypical or secondary parkinsonism as determined by referring Neurologist
- Other disorders that might interfere with ability to perform high intensity endurance exercise (e.g. history of stroke, respiratory problems, traumatic brain injury, known advanced osteoarthritis, or neuromuscular disease).
- Individuals with known injury, disease, or condition that would affect the ability to perform endurance exercise.
- Any other clinically significant medical condition, psychiatric condition, drug or alcohol abuse that would, in the judgment of the investigator, interfere with the subject's ability to participate in the study.
- "Vigorous athletes" participating in any exercise program 2X/week or more will be excluded.
- Individuals with any type of implanted electrical device (such as a cardiac pacemaker or a neurostimulator), or a certain type of metallic clip

PROTOCOL TITLE: Mild Cognitive Impairment and Endurance Exercise in Parkinson's Disease

(i.e., an aneurysm clip in the brain) are not eligible for participation in the MRI study.

- Persons who have had a long history of working in metal shops will be excluded unless they have had a previous orbital x-ray scan clearing them for participation in MRI studies.
- Females who are pregnant or might be pregnant will be excluded from participation.
- Individuals who are claustrophobic and unable to tolerate a brain MRI scan will be excluded.
- Treatment with cholinesterase inhibitors or memantine (i.e., medications approved for treatment of dementia) or medications affecting cognition (i.e., anticholinergics)
- Use of medications that might interfere with neuromuscular junction function such as D-penicillamine and aminoglycoside antibiotics.
- Use of medications that might interfere with the BOLD contrast or heart response to exercise (e.g. β blockers).
- Individuals at high risk for cardiovascular disease as defined in Table 2.2 by the new ACSM guidelines.(Medicine 2014)
- Younger than 40 and older than 85. We exclude participants younger than 40 because these young onset patients may not be typical of the majority of patients who get the disease later in life. We exclude participants older than 85 because of the limited evidence they can successfully complete a high-intensity endurance exercise program. We also exclude patients whose disease was diagnosed before the age of 40.
- Individuals with known endocrine abnormalities or steroid use that could affect cortisol levels (e.g., Cushing's syndrome, pituitary or adrenal gland disease or adrenalectomy, use of steroid-based medications.
- Individuals with strong history of chronic inflammatory or autoimmune diseases or history of chronic use of NSAIDs, which could cause abnormal levels of inflammatory markers in the plasma.

3.3 We will exclude adults unable to consent, individuals who are not yet adults, pregnant women, prisoners and children from this study.

4.0 Study-Wide Number of Subjects: NA (not a multicenter study)

5.0 Study-Wide Recruitment Methods: NA

6.0 Multi-Site Research: NA

7.0 Study Timelines

PROTOCOL TITLE: Mild Cognitive Impairment and Endurance Exercise in Parkinson's Disease

- 7.1 The duration of an individual subject's participation in the study will be 6 months. Achieving full participant accrual will require enrolling up to 16 participants over 18 months. The estimated date for the investigators to complete this pilot study is January 1, 2017.

8.0 Study Endpoints

8.1 Primary endpoints:

The primary endpoint will be the mean change in cognitive function from baseline to 6-months as measured by global statistical test (GST) for attention/working memory, executive function, memory, and processing speed. The GSTs will be calculated from the following tests reflecting specific cognitive domains and administered in the cognitive test battery (Attention/working memory, Executive function, Memory, Processing Speed) including:

Symbol Digit Modality Test,(Smith 1973)

Trail Making Test-Parts A and B,(Reitan and Wolfson 1993)

Raven's Progressive Matrices,(Raven, Raven et al. 2003)

Clock Drawing,(Goodglass and Kaplan 1983)

Hopkin Verbal Learning Test-Revised (Word list learning and delayed recall),(Brandt and Benedict 2001)

Free and Cued Selective Reminding Test,(Grober and Buschke 1987)

Figural memory test,(Wilson, Gilley et al. 2000)

Secondary endpoints:

The secondary endpoints will include the following:

- a) Change from baseline to 6-months for clinical, behavioral, and additional cognitive measures including the following:
- 1) Sleep (Pittsburgh Sleep Quality Index)(Buysse, Reynolds et al. 1989), (Epworth Sleepiness Scale),(Johns 1991)
 - 2) Fatigue (Fatigue Severity Scale),(Krupp, LaRocca et al. 1989)
 - 3) Mood (Hamilton Depression Scale),(Hamilton 1967)
 - 4) PD Neurol QOL (NINDS 2015) and Health-related quality of life (PDQ-39),(Hagell and Nilsson 2009)
 - 5) additional cognitive tasks
 - Language:
 - Boston Naming Test,(Kaplan 1983)
 - Verbal fluency [semantic - animals, phonemic - letters]; {Morris, 1989 #47
 - Visuospatial:
 - Judgment of Line Orientation, {Benton, 1978 #35
 - Intersecting pentagons; {Bourke, 1995 #36}.

PROTOCOL TITLE: Mild Cognitive Impairment and Endurance Exercise in Parkinson's Disease

- b) Change from baseline to 6-months for motor function including the following:
- 1) Movement Disorder Society Unified PD Rating Scale [MDS-UPDRS] part III motor score,(Goetz, Tilley et al. 2008)
 - 2) Mini Balance Evaluation Systems Test (mini-BESTest) (Franchignoni, Horak et al. 2010)
 - 3) Timed up and go (TUG) (Morris, Morris et al. 2001, Huang, Hsieh et al. 2011)
 - 4) The six-minute walk test (6MWT) (Schenkman, Ellis et al. 2011)
 - 5) The Activities-Specific Balance Confidence Scale (ABC) (Dal Bello-Haas, Klassen et al. 2011)
 - 6) The New Freezing of Gait Questionnaire (NFOG-Q)(Nieuwboer, Rochester et al. 2009)

Participants will wear an activity monitor for one week per month. This will allow us to collect average physical activity across one week time periods which will be used to analyze the impact of the intervention outside of the structured exercise sessions of the endurance exercise group. This will allow us to determine if the endurance exercise group alters its overall activity level over the 6 month time period.

- c) Change from baseline to 6-months for brain imaging measures including the following:
- 1) Hippocampal volumes on structural MRI,
 - 2) Microstructural integrity of white matter pathways on diffusion tensor imaging (DTI),
 - 3) Functional connectivity among brain networks on resting state fMRI,
 - 4) Responses to task-based fMRI Digit Symbol Substitution Test.
- d) Change from baseline to 6-months for biospecimen measures including the following:
- 1) Salivary cortisol measurements; in addition, changes in salivary cortisol measures collected over 8 time points on two consecutive days will be explored at the pre-test and the post-test. We will measure cortisol at time points 0 minutes, 15 minutes, 30 minutes, 45 minutes after the person wakes up.(Stalder, Kirschbaum et al. 2016) In addition, we will measure cortisol at 3 hours, 6 hours, 9 hours and 12 hours after awakening.(Edwards, Clow et al. 2001)
 - 2) Soluble inflammatory biomarkers in plasma
 - 3) Peripheral levels of neurotrophic factors in plasma

PROTOCOL TITLE: Mild Cognitive Impairment and Endurance Exercise in Parkinson's Disease

e) We will collect the NINDS common data elements (CDE) for sex, ethnicity, date-of-birth, education level, family history, and employment status.

- 8.2. Safety Endpoints: There are no safety endpoints, but all participants will be monitored for safety and for adverse events.

Adverse Events (AEs) are defined as exercise-related discomforts (e.g., muscle and joint soreness/pain), minor injuries (e.g., strains, sprains), and non-injurious falls; and attrition is defined as the number of participants who withdraw from the study. Serious Adverse Events (SAEs) are defined as hospitalization, surgery, death, or permanent disability. We will keep detailed logs of all the training sessions so that we can monitor their progress in the endurance exercise program and assess compliance, which we will take to be completion of 80% of the prescribed exercise sessions.

All participants will be prescreened for MRI scans as per Radiology guidelines to ensure MRI safety including screening for cardiac pacemakers, metal implants of any kind in the body, pregnancy, among other conditions.

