 5. MOCA
 6. Pittsburgh Sleep Quality Index,
 7. Epworth Sleepiness Scale,
 8. Fatigue Severity Scale,
 9. Hamilton Depression Scale,
 10. Health-related quality of life (PDQ-39),
 11. Mini Balance Evaluation Systems Test
 12. Timed up and Go (3 trials)
 13. Six-minute walk test
 14. Activities-Specific Balance Confidence Scale
 15. New Freezing of Gait Questionnaire
 16. MoCA Alternate version
 17. Symbol Digit Modality Test,
 18. Trail Making Test-Parts A and B,
 19. Raven's Progressive Matrices,
 20. Clock Drawing,
 21. Hopkins HVLN-R,
 22. Free and Cued Selective Reminding Test,
 23. Figural memory test, ,
 24. Boston Naming Test,
 25. Verbal fluency [semantic - animals, phonemic - letters],
 26. Judgment of Line Orientation,
 27. Intersecting pentagons,

9.4 The data that will be collected is outlined in Table 1.

PROTOCOL TITLE: Mild Cognitive Impairment and Endurance Exercise in Parkinson’s Disease

Table 1 Dependent Measures	Baseline	Each ex session	Each mo	6 mo
Primary Measures				
Cognitive Measures: Symbol Digit Modality Test, Trail Making Test-Parts A and B, Raven’s Progressive Matrices, Clock Drawing, Word list learning and delayed recall, Free and Cued Selective Reminding Test, Figural memory test,	X			X
Secondary Measures				
National Institute of Neurological Disorders and Stroke common data elements	X			
MDS-UPDRS I, II, IV	X			X
Sleep (Pittsburgh Sleep Quality Index, Epworth Sleepiness Scale)	X			X
Fatigue (Fatigue Severity Scale)	X			X
Mood (Hamilton Depression Scale)	X			X
PDQ-39	X			X
Cognitive Measures: Boston Naming Test, Verbal Fluency, Judgment of Line Orientation, Intersection pentagons, Spatial working memory	X			X
MDS-UPDRS III	X			X
Neuro-QOL	X			X
Mini Balance Evaluation Systems Test (Mini-BESTest)	X			X
Timed Up and Go	X			X
6 minute walk test	X			X
Activities-Specific Balance Confidence Scale (ABC scale)	X			X
New Freezing of Gait Questionnaire (NFOG-Q)	X			X
Activity Monitor			X	
MRI: Hippocampal volumes	X			X
MRI: DTI measures	X			X
MRI: Functional connectivity	X			X
Serious Adverse Events (SAEs) and Adverse Events (AEs)			X	
Attrition			X	
EE training log		X		
Levodopa Equivalent	X			X
Cortisol (2 consecutive time points)	X (8)			X (8)
Blood Draw	X			X

PROTOCOL TITLE: Mild Cognitive Impairment and Endurance Exercise in Parkinson's Disease

10.0 Data and Specimen Banking:

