11.0 Data and Specimen Management

- 11.1* We are collecting pilot data primarily for feasibility, though statistical analyses may be conducted to provide descriptive data of the subject cohort, baseline and 6-month test scores, and potentially exploratory analyses of change in outcome measures or correlations of variables.
- 11.2* Since we are collecting pilot data, there is no power analysis.

PROTOCOL TITLE: Mild Cognitive Impairment and Endurance Exercise in Parkinson's Disease

- 11.3* The research will be conducted in compliance with state and federal laws, including the Health Insurance Portability and Accountability Act (HIPAA) that require researchers to protect and maintain confidentiality of an individual's health information. All subjects will be asked to sign an "Authorization To Use and Disclose (Release) Health Information For a Research Study". Access to all study datasets will be password protected. All research staff will be trained in proper research procedures. We have extensive experience in data capture, data flow and data management based on our SPARX Phase II clinical trial.(Moore, Schenkman et al. 2013) We will use REDCap (Research Electronic Data Capture) to define and manage our own data collection forms. This service is provided through the Northwestern University Clinical and Translational Institute.
- 11.4* Quality control is addressed at the point of data collection, data entry, and data analysis.
- Imaging – the imaging center conducts tests for quality control of the imaging data. A quality control scan is run every day before data acquisition begins.
 - All of our data is double checked for accuracy by a member of our research team. Periodically we have our data checked by a person who is not directly involved in the laboratory.
- 11.5* Study-wide handling of data and specimens is described below:
- Our data consists of analog data and text.
 - Our data is stored on hard disks and backed up regularly.
 - Our data is stored indefinitely.
 - The clinical coordinator, statistician and students and post- doctoral fellows will have access to the data.
 - The clinical coordinator is responsible for receipt of the data.
 - The data will not be transported.
 - The cortisol data will initially stored in a freezer at -80°C before being shipped out for analysis.

12.0 Provisions to Monitor the Data to Ensure the Safety of Subjects:

This study does not involve more than minimal risk.

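### Does the primary cognitive endpoint need changing because it includes processing speed, a domain that Hypothesis 1 does not name?

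*Combined protocol and SAP*

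**What the plan says.** Aim 1 (Section 1.1) concerns the effect of exercise on cognition in general and names no domain. Hypothesis 1 (Section 1.2) is narrower: exercise "will improve cognitive function, specifically attention, executive function and memory in PD-MCI patients".

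Section 8.1 sets the primary endpoint as mean change from baseline to six months "as measured by global statistical test (GST) for attention/working memory, executive function, memory, and processing speed". The next sentence moves to the plural: "The GSTs will be calculated from the following tests reflecting specific cognitive domains". Seven test entries follow: Symbol Digit Modality Test (SDMT), Trail Making A and B, Raven's matrices, clock drawing, Hopkins verbal learning (learning and delayed recall), Free and Cued Selective Reminding, and figural memory. No test is assigned to a domain, and no weights or scoring rule are given. The same instruments appear in the primary row of Table 1 (Section 9.4) and in the Day 3 battery (Section 9.2).

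On use, Section 2.2 says "The purpose of this IRB is to collect pilot data for a subsequent R01". Section 11.1 says "We are collecting pilot data primarily for feasibility, though statistical analyses may be conducted to provide descriptive data of the subject cohort", and it also mentions "potentially exploratory analyses of change in outcome measures or correlations of variables". Section 11.2 states that there is no power analysis.

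The secondary row of Table 1 reads "Cognitive Measures: Boston Naming Test, Verbal Fluency, Judgment of Line Orientation, Intersection pentagons, Spatial working memory". Its last item is not in Section 8.1, the Day 3 battery or the form list in Section 9.3.

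**The concern.** Processing speed is named only in Section 8.1; no aim, hypothesis or background text mentions it. If the global statistical test (GST) is one pooled score, a domain outside the hypothesis can mislead in two ways. If speed does not move, the pooled change is smaller than the change in the three hypothesised domains. If only speed moves, the primary endpoint improves although nothing in Hypothesis 1 has happened. If there is one GST per domain, one of four primary scores has no hypothesis behind it.

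Section 8.1 also leaves open whether SDMT, Trail A or both count as speed, so two analysts could follow it faithfully and report different primary figures. Since the pilot is meant to feed a larger grant application, a diluted effect size might be carried into the size of the next trial.

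**Working it through.** The documents give no effect size, standard deviation, weight or power figure, so there is no stated figure to reproduce. The question is how far the fourth domain could move a pooled score.

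**1. Mean change.** Suppose one equally weighted mean of m standardised components, of which k measure speed. Let r be the change in speed divided by the change in the named domains. Then

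shortfall = 1 − [(m − k) + k·r]/m = (k/m)(1 − r).

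The counts m come from Section 8.1: four domains; seven test entries; eight scores if Trails A and B are split; nine if Hopkins learning and recall are split too. Both k and r are assumptions.

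| Reading | k/m | r = 0 | r = 0.5 | r = 1 |
|---|---|---|---|---|
| Four domains | 1/4 | 25.0% | 12.5% | 0% |
| Seven entries, SDMT as speed | 1/7 | 14.3% | 7.1% | 0% |
| Seven entries, SDMT and Trails | 2/7 | 28.6% | 14.3% | 0% |
| Eight scores, SDMT | 1/8 | 12.5% | 6.25% | 0% |
| Eight scores, SDMT and Trail A | 2/8 | 25.0% | 12.5% | 0% |
| Nine scores, SDMT | 1/9 | 11.1% | 5.6% | 0% |
| Nine scores, SDMT and Trail A | 2/9 | 22.2% | 11.1% | 0% |
| Nine scores, SDMT and both Trails | 3/9 | 33.3% | 16.7% | 0% |

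If one GST is reported per domain, the shortfall is 0% for each named domain whatever r is.

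**2. Standardised effect.** Take equally weighted domains with equal change variance and common correlation p (all assumed). The four-domain effect size divided by the three-domain one is

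R = [(3 + r)/4] × √{4(1 + 2p) / [3(1 + 3p)]},

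and a later trial sized on it would need 1/R² times as many people.

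| p | R, r = 0 | 1/R² | R, r = 1 | 1/R² |
|---|---|---|---|---|
| 0 | 0.866 | 1.33 | 1.155 | 0.75 |
| 0.3 | 0.795 | 1.58 | 1.060 | 0.89 |
| 0.5 | 0.775 | 1.67 | 1.033 | 0.94 |
| 1 | 0.750 | 1.78 | 1.000 | 1.00 |

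The direction depends on r: adding speed costs efficiency if speed is inert, and costs nothing or helps a little if speed gains equally.

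**3. Against sampling error.** With 16 completers, the 95% half-width for mean change is 2.131/√16 = 0.533 SD of the composite's change. In SDs of a single domain's change, multiply by √[(1 + 3p)/4]: 0.27 at p = 0, 0.42 at p = 0.5, 0.53 at p = 1. For an assumed gain of 0.5 SD in each named domain and none in speed, the four-domain shortfall is 0.25 × 0.5 = 0.125 SD, less than half the half-width even at p = 0. Section 23.3 counts drop-outs and screen failures within the 16, so completers may be fewer and the interval wider.

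**The case for a change.** The best case for a change is textual. The word that introduces the three domains in Hypothesis 1 reads as limiting, the endpoint then adds a fourth, and nothing elsewhere reconciles the two. Section 8.1 leaves the composite open enough for different analysts to reach different primary figures. Pilot status lowers the stakes without removing the mismatch, and aligning the text would cost only wording.

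The mismatch stands, and so does the missing scoring detail. The claim of a loss of a particular size does not. Hypothesis 1 is silent on speed; it does not predict zero change there. A dilution figure needs a single pooled score, a set of weights, an inert speed domain and a test-to-domain map, and the documents supply none of these. The plural GSTs is at least compatible with separate domain scores, in which case nothing is diluted. Nor do the documents say that the later trial would be sized on this composite.

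**Conclusion.** No change to the plan follows. Hypothesis 1 and Section 8.1 do differ by one domain, but an endpoint somewhat broader than its hypothesis still fits Aim 1, and all three named domains are in it. The size of any dilution cannot be fixed from the documents: 0% to about 33% of the mean change, with a standardised-effect ratio anywhere from 0.75 to 1.15 for four equally weighted domains as r runs from 0 to 1.

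Neither way of aligning the text is a clear gain. Adding speed to the hypothesis alters no result. Removing it from the composite is a debatable trade: the tests most readily taken as speed may also be those that carry attention, which could be left thinly measured.

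The scoring rule, weights, direction and handling of missing tests are details that an analyst can settle sensibly. Each test is recorded on its own form, so domain-level changes, or the composite with and without speed, can be shown whenever wanted. Section 11 puts feasibility first, makes analyses of change optional and exploratory, and gives no power analysis; no decision rule rests on the GST. Spatial working memory in Table 1 is a clerical slip that touches no primary measure.

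This conclusion rests on the pilot being reported as Section 11.1 describes it. It would not carry over to a confirmatory trial with the same endpoint text.
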